A phase IV, randomized, double-masked, active controlled, within-subject equivalency clinical trial to compare effectiveness and safety of Lunaphil Ultra (Hyaluronic acid, produced by Espad Pharmed Co.) versus Juvéderm® Ultra 4 (Hyaluronic acid, produced by Allergan Co.) for the management of moderate or severe nasolabial folds (NLFs)

Ethics Approval Number

IR.TUMS.MEDICINE.REC.1400.1011

SAP Version (SAP version number with dates)

Version: 1.0, Date: 2021 August 14

Section 2: Introduction

Introduction

This Statistical Analysis Plan (SAP) provides a detailed and comprehensive description of the planned statistical analyses for the Phase IV randomized, double-blind, parallel-group, active-controlled clinical trial designed to assess the therapeutic equivalence in efficacy and safety of Lunaphil Ultra (Hyaluronic acid, produced by Espad Pharmed Co.) versus Juvéderm® Ultra 4 (Hyaluronic acid, produced by Allergan Co.) in managing moderate or severe NLFs.

The objective of this SAP is to outline the statistical methodologies and analysis principles that will be applied to evaluate the primary and secondary endpoints of the study, as well as the handling of missing data, analysis sets, and subgroup analyses. This SAP is intended to ensure transparency and reproducibility of the planned analyses, and it has been finalized prior to database lock and unblinding of the study data.

Rationale and Background

Skin aging is a complex and multifactorial process resulting in various functional and aesthetic changes in the skin (1). It is an inevitable process that can be described clinically as features of wrinkles, sun

spots, uneven skin color, and sagging skin (2). Additional clinical findings include tear trough, a drop of the angle of the mouth, loss of definition in the mandibular border, platysmal bands, evident veins, and NLFs as one of the typical clinical manifestations of facial aging (3).

The perception of health and age is a critical aspect in the common judgment of attractiveness and people are judged to be less attractive as they age (4). Attractiveness influences both self-perception and social behavior and is related to traits such as self-confidence and social acceptance. Therefore, aesthetic interventions can improve psychological well-being and quality of life (5).

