3. The injected volume to obtain optimal aesthetic result (initial treatment + touch-up)
4. The number of NLFs receiving touch-up treatment
5. The incidence, severity and causal relationship of adverse events

Section 3: Research Methods

Study Design

This is a randomized, double-masked, active controlled, within-subject, and equivalency study to compare the effectiveness and safety of Lunaphil Ultra (Hyaluronic acid, produced by Espad Pharmed Co.) versus Juvéderm® Ultra 4 (Hyaluronic acid, produced by Allergan Co.) for the management of moderate or severe NLFs.

Intervention

Subjects will be treated with Juvéderm® Ultra 4 in one NLF and Lunaphil Ultra in the opposite NLF. Two treatments will be allowed over a 2-week period (initial treatment plus one touch-up) to achieve optimal correction of the NLFs. The level of correction will be assessed by the evaluating investigator at week 2 after the initial treatment and, if less than optimal, the treating investigator will be directed to retreat the undercorrected NLF(s).

Randomization

The subjects will be randomized into two possible treatment groups. The first treatment group will receive Lunaphil Ultra on the right side and Juvéderm® Ultra 4 on the left side of their face. The second treatment group will receive Juvéderm® Ultra 4 on the right side and Lunaphil Ultra on the left side of their face. The randomization plan of the subjects will be carried out centrally using an R-CRAN software version 4.0.3. Blocks (with the size of 2) will be made using permuted block randomization for a total of 108 subjects (1:1 allocation ratio).

Blinding

To prevent any bias arising from awareness of face-side allocation, this study will be performed in a double-blind manner. For each participant, one side of the face will receive the investigational hyaluronic acid product and the other side will receive the reference Hyaluronic acid product, according to the pre-specified randomization plan. Both the participants and all investigators responsible for administering injections and assessing outcomes will remain blinded to the allocation throughout the study.

Sample size

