4. Not possible to follow the participant's condition (Loss to follow-up)

5. Change in participant's conditions, which needs change of treatment due to investigator decision or administration of prohibited medications in the protocol

Data sources and measurement

All data will be collected by specialists and recorded in a booklet comprising five visits. Baseline information (demographics, past medical history, history of filler injection, patients' medications), intervention information (e.g., dosage at visit 1 and touch up), WSRS, and PGAIS will be recorded.

All adverse events (AEs) will be documented and categorized according to their frequency, severity (graded using the Common Terminology Criteria for Adverse Events version 5.0) (14), and their assessed causality, following the World Health Organization guidelines (15). The AEs will be reported using the Medical Dictionary for Regulatory Activities (MedDRA) under both the preferred term (PT) and system organ class (SOC) (16). Serious adverse events (SAEs) will be documented in compliance with the E2B(R2) guideline (17) and will be defined as any AE that “results in death, is life-threatening, requires inpatient hospitalization or prolongation of existing hospitalization, results in persistent or significant disability/incapacity, is a congenital anomaly/birth defect, or other medically important condition.”

Section 4: General issues for statistical analysis

Analysis populations

Primary efficacy will be analyzed on a per-protocol population. Also, the primary outcome and secondary key variables of the study will be examined on the intention-to-treat population, and sensitivity analysis will be used to compare the primary outcome in the two populations. All analyzes of complications will be performed based on the safety population.

1. Per-protocol population: all patients who were randomly treated with the study drug and did not have a major deviation from the protocol.
2. Intention-to-treat population: all patients randomly assigned to one of the treatment groups. Patients are analyzed according to the treatment they received randomly.
3. Safety population: All patients who randomly received at least one dose of the study drug. Patients are analyzed according to the treatment they actually received.

Protocol violations and deviations

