Descriptive statistics for baseline characteristics will be presented as mean and standard deviation for continuous variables, and as frequency and percentage for categorical variables.

Section 7: Statistical Analysis

This section describes the planned statistical analyses for efficacy and safety outcomes. Results will be summarized using appropriate descriptive statistics and analyzed using suitable statistical models depending on the data type. Treatment effects will be presented with 95% confidence intervals and two-sided p-values, using a significance level of 0.05.

Primary Endpoint Analysis

For the statistical analysis of the primary outcome (equivalence assessment of the mean level of improvement from baseline in NLFs severity score), both categories of Per-Protocol and Intention-to-Treat statistical population will be examined. Although the main approach is the results of the statistical analysis of the Per-Protocol population, eventually a sensitivity analysis will be performed between the results of the said analysis and the results of the statistical analysis of the Intention-to-Treat population.

Paired t-test or a signed-rank test will be used to compare the mean level of improvement from baseline in NLFs severity score based on assessments by evaluating investigators between Lunaphil Ultra (Hyaluronic acid, produced by Espad Pharmed Co.) compared to Juvéderm® Ultra 4 (Hyaluronic acid, produced by Allergan Co.). The 95% confidence interval (CI) for the mean difference between the two treatments will be calculated. Equivalence will be concluded if the entire 95% CI falls within the pre-specified equivalence margin of ± 0.17 .

Secondary Endpoints Analysis

- The number of patients with improvement score for the PGAIS will be analyzed using a McNemar test.
- The proportion of NLFs maintaining a clinically significant improvement will be analyzed using a McNemar test.
- Injection volume to obtain optimal result will be analyzed with a paired t-test or a signed-rank test.

The number of NLFs receiving touch-up treatment will be analyzed using a McNemar test.

Safety Analysis

All adverse events (AEs) data will be descriptively analyzed. Also, AEs in two groups are compared

using Pearson chi-square test.

The incidence and percentage of treatment-emergent adverse events will be reported, categorized by system organ class (SOC) and preferred term (PT). Adverse events' severity, seriousness, and causality assessment will be reported.

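### Adverse events are compared with an unpaired chi-square test although every participant receives both products

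*SAP*

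**What the plan says.** The Safety Analysis part of SAP Section 7 opens with "All adverse events (AEs) data will be descriptively analyzed" and then adds a formal comparison: "Also, AEs in two groups are compared" "using Pearson chi-square test". It does not say what the two groups are.

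The design is within-subject. SAP Section 3 (Intervention) states: "Subjects will be treated with Juvéderm® Ultra 4 in one NLF and Lunaphil Ultra in the opposite NLF". The Setting part of the protocol abstract says the same.

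The other binary outcomes in SAP Section 7 (PGAIS improvement, clinically significant WSRS improvement, touch-up) all get a paired test, for example: "The number of NLFs receiving touch-up treatment will be analyzed using a McNemar test". The WSRS change and injection volume get a paired t-test or signed-rank test. The adverse event comparison is the only unpaired test in the plan.

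Protocol section 8.7.2 and the SAP synopsis name only summary statistics for safety and no test.

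**The concern.** Pearson's chi-square treats 108 participants as 216 independent folds. Two folds on one face share skin, injection session and aftercare, so local reactions on them may well be correlated. If the correlation is positive, the test uses too large a standard error. It then rejects too rarely and gives up the precision that the split-face design was chosen to provide. If it is negative, the test rejects too often.

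The trial sets out to show that two products are alike. An error that favours a finding of no significant difference in injection-site reactions, the adverse events named as an outcome in protocol section 8.4, therefore leans towards the desired conclusion.

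The sentence is also undefined in two respects: which groups are compared, and what happens to events such as headache that belong to neither fold.

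**Working it through.** **1. What the two groups could mean.**

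- *By product.* The safety population rule in SAP Section 4, "Patients are analyzed according to the treatment they actually received", puts every fully treated participant under both products. The data are paired, so the test is the wrong one.
- *By randomised group.* SAP Section 3 says "The subjects will be randomized into two possible treatment groups", but these groups are the two side sequences. They are independent, yet both receive both products, so comparing them does not compare products.
- *Events not tied to a fold.* These have no product contrast in this design, yet the sentence covers adverse events without restriction.

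No reading makes the sentence work.

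**2. Inputs.** The documents give N = 108 and a two-sided 0.05 level (SAP Section 7). The N follows from the primary endpoint: 97 / 0.9 = 107.8, rounded up to 108, and exact paired TOST power at n = 97 (SD 0.510, margin ±0.170, 2.5% per side) is 80.3%, so the stated 80% is reproduced. There is no stated power, event rate or correlation for adverse events. The rates and phi below are assumptions.

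**3. False-positive rate at equal rates p.** For the difference in proportions over n pairs:

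- variance used by Pearson: 2p(1−p)/n
- true variance: 2p(1−p)(1−phi)/n
- ratio of standard errors: 1/√(1−phi), which is 1.20 at phi 0.3 and 1.41 at phi 0.5
- rejection rate: P(|Z| > 1.96/√(1−phi))

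| phi | 1.96/√(1−phi) | Closed form | Simulated, p = 30% |
|---|---|---|---|
| −0.2 | 1.79 | 7.4% | 7.4% |
| 0 | 1.96 | 5.0% | 5.0% |
| 0.3 | 2.34 | 1.9% | 2.0% |
| 0.5 | 2.77 | 0.6% | 0.6% |

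**4. Power for 40% versus 28%.** These are 400,000 simulated paired tables per setting. The probability of a reaction on both folds is p1·p2 + phi·√(p1(1−p1)p2(1−p2)).

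| phi | Pearson | McNemar, asymptotic | McNemar, exact |
|---|---|---|---|
| 0 | 46.9% | 45.8% | 40.8% |
| 0.3 | 46.0% | 60.4% | 53.3% |
| 0.5 | 45.0% | 76.5% | 68.1% |

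Relative to a paired test, Pearson gives up about 7 to 14 points at phi 0.3 and 23 to 32 points at phi 0.5. At phi 0 it gives up nothing.

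**5. Invented example.** Suppose 48 Lunaphil folds and 36 comparator folds react, a difference of 12/108 = 11.1 points. The pooled rate is 84/216 = 0.389, so Pearson's statistic is 0.1111² / (0.389 × 0.611 × 2/108) = 2.81, p = 0.094, whatever the pairing.

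| Both / Lunaphil only / comparator only / neither | phi | Exact McNemar p |
|---|---|---|
| 30 / 18 / 6 / 54 | 0.55 | 0.023 |
| 25 / 23 / 11 / 49 | 0.36 | 0.058 |
| 16 / 32 / 20 / 40 | 0 | 0.126 |

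In the first table the paired Wald standard error is √(24 − 12²/108)/108 = 0.0441, giving a 95% CI of 2.5 to 19.8 points. The unpaired standard error is 0.0659, giving −1.8 to 24.0 points.

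**The case against.** The strongest counter-argument is that little depends on this test. The protocol and the SAP synopsis treat safety with summary statistics, SAP Section 7 starts with description, and the observed rates by product are the same under either test. That stands and limits the seriousness of the point.

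Second, Pearson's power in the example hardly changes with phi (46.9% to 45.0%). This is correct: what is lost is the gain a paired test would have brought, so the loss is relative to McNemar.

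Third, every rate and correlation here is assumed, and the larger losses need phi near 0.5. At phi 0.36 in the worked example, exact McNemar also stays above 0.05. This stands too. Positive correlation is plausible but not documented.

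Fourth, exact McNemar is itself conservative. At 30% rates and phi 0.3 its size is 3.2%, against 2.0% for Pearson. At 5% rates both are below 2%. For 6% versus 2% at phi 0.3 it has no power advantage (23–24% against 27%). So it does not cure the conservatism for rare events.

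None of this makes an independent-groups test valid for paired folds.

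**Conclusion.** The point holds. The planned test does not fit the design, it departs from the SAP's own handling of its other binary outcomes, and no reading of the two groups rescues it. The test is miscalibrated whenever reactions on the two folds are correlated: conservative if phi is positive, too liberal if negative, and close to nominal at phi 0. Under the assumed rates, the power forgone against a paired test ranges from none at phi 0 to 23–32 points at phi 0.5.

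This should be corrected before the analysis, but it does not threaten the trial's main result. The equivalence conclusion and the sample size of 108 do not depend on it.

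**What to change.** Replace the chi-square sentence in SAP Section 7 with text to this effect: *Injection-site adverse events recorded by fold will be compared between products with McNemar's test, and the paired risk difference will be given with a 95% CI. Concordant and discordant counts will be shown. Adverse events that cannot be attributed to a fold will be counted once per participant and described without a between-product test.*

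Three details should be settled in the same sentence:

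- **Version of the test.** Either use the exact version throughout, or state the number of discordant pairs below which it applies.
- **Interval method.** Name it. In the 25/23/11/49 example a Wald interval (0.7 to 21.5 points) excludes zero while the exact p is 0.058, so test and interval can disagree. State which is primary.
- **Scope.** Say whether the test applies to any injection-site event or to each preferred term, since SAP Section 4 plans no multiplicity adjustment.

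A simpler alternative is to delete the test and report only descriptive rates, with or without paired risk differences. That would match protocol section 8.7.2 and the SAP synopsis.

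The SAP Introduction calls this a "Phase IV randomized, double-blind, parallel-group, active-controlled clinical trial". The parallel-group label should be removed so that the SAP describes one design. The by-arm disposition tables in SAP Section 6 should be checked for the same reason.

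The cost is one sentence and one label, with no change to sample size, visits or treatment. The sponsor must confirm that injection-site events are recorded by fold. Neither document says so, but any comparison by product already needs it.
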